12.4.5 Assessment of Stabilization of ECL

12.4.5.1 Statistical Hypotheses

No hypothesis testing of the endpoint is planned.

12.4.5.2 Analysis Methods

The annualized rate of change and percent rate of change in central endothelial cell density will be summarized at each year of observation. A 95% confidence interval based on the t-distribution will be produced along with the mean, standard deviation, minimum, median and maximum. This analysis will be performed using central endothelial cell density data from visits in the COMPASS, COMPASS XT, and COMPASS XXT studies, where available.

12.4.6 Corneal Sequelae Associated with ECL

12.4.6.1 Statistical Hypotheses

No hypothesis testing of the endpoint is planned.

12.4.6.2 Analysis Methods

A listing of corneal sequelae associated with ECL will be provided.

12.4.7 Association between Peripheral and Central ECD Count and Number of Observed Rings

12.4.7.1 Statistical Hypotheses

No hypothesis testing of the endpoint is planned.

12.4.7.2 Analysis Methods

Summary statistics for peripheral ECD count will be provided, stratified by visit and by number of rings observed at the visit, for all COMPASS XXT study visits. Summary statistics for central ECD count will be provided, stratified by the number of rings observed at the

Document: TDOC-0056258 Version: 3.0; Most-Recent; Effective; CURRENT

Status: Effective Page 47 of 57

visit, for all visits with available data from the COMPASS, COMPASS XT, and COMPASS XXT studies.

12.4.8 Secondary Surgical Interventions (SSIs) to Modify the Device Position (eg, Repositioning, Trimming, Explanation)

12.4.8.1 Statistical Hypotheses

No hypothesis testing of the endpoint is planned.

12.4.8.2 Analysis Methods

A listing of SSIs to modify the device position will be provided.

12.4.9 Effects of SSIs on Central and Peripheral ECD

12.4.9.1 Statistical Hypotheses

No hypothesis testing of the endpoint is planned.

12.4.9.2 Analysis Methods

A listing of central and peripheral ECD measurements will be produced for subjects with SSIs. The date of the SSI will be noted in this listing for each subject.

12.4.10 CyPass Micro-Stent Movement and/or Malposition

12.4.10.1 Statistical Hypotheses

No hypothesis testing of the endpoint is planned.

12.4.10.2 Analysis Methods

The rate of all CyPass Micro-Stent movement and/or malposition will be presented with a count and percentage, and will be accompanied by a two-sided exact binomial 95% confidence interval.

12.4.11 Corneal AEs (eg, Corneal Decompensation, Tube Corneal Touch, Corneal Edema, etc.) Caused by CyPass Micro-Stent

12.4.11.1 Statistical Hypotheses

No hypothesis testing of the endpoint is planned.

Document: TDOC-0056258 Version: 3.0; Most-Recent; Effective; CURRENT

Status: Effective Page 48 of 57

12.4.11.2 Analysis Methods

A listing of corneal AEs caused by the CyPass Micro-Stent will be provided, which will include central and peripheral ECD measurements, where available.

12.4.12 Losses in Best Corrected Visual Acuity (BCVA) \geq 10 letters

12.4.12.1 Statistical Hypotheses

No hypothesis testing of the endpoint is planned.

12.4.12.2 Analysis Methods

A listing of BCVA loss of 10 letters or more will be provided, and will include all available BCVA data from the COMPASS, COMPASS XT, and COMPASS XXT studies for the subject. BCVA loss of 2 lines (10 letters) or more will be reported as an adverse event, so adverse event data will be the data source for this analysis.

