10.2.6 Best Corrected Visual Acuity: Safety Assessment

Perform monocular BCVA testing using ETDRS for the study eye at all study visits (84-Month Visit [±120 days] to 120-Month Visit [±120 days]) prior to any assessment

Document: TDOC-0056258 Version: 3.0; Most-Recent; Effective; CURRENT

Status: Effective Page 31 of 57

requiring administration of eye drops to dilate the eyes, or any assessment requiring contact with the eye. This assessment must be performed study personnel who have successfully completed the training required to conduct the assessment.

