11.1.1 Postoperative Adverse Events

Anticipated postoperative AEs include, but are not limited to, the following complications.

Document: TDOC-0056258 Version: 3.0; Most-Recent; Effective; CURRENT

Status: Effective Page 36 of 57

a) BCDVA loss of 2 lines (10 letters) or more on the ETDRS chart in comparison with the best BCDVA reported in COMPASS/COMPASS XT

- b) Persistent (at time of study exit) BCDVA loss of 3 or more lines compared to best BCDVA achieved during the course of study, including both the COMPASS trial, and the COMPASS XT trial
- c) 2-point worsening to severe on the slit-lamp examination findings (other than cells and flare) not associated with a pre-existing condition
- d) Endophthalmitis
- e) Flat AC with lens cornea touch
- f) Shallow AC with iridocorneal apposition
- g) Shallow AC with peripheral iridocorneal apposition
- h) Aqueous misdirection
- i) Chronic iritis
- j) Conjunctivitis
- k) Keratitis
- 1) Corneal edema
- m) Corneal opacification
- n) Corneal decompensation
- o) Hyphema (defined as persistent hyphema of ≥ 2 mm)
- p) Vitreous hemorrhage
- q) Retinal detachment
- r) Other retinal complications (eg, dialysis, flap tears, or proliferative vitreoretinopathy)
- s) Increase in C:D ratio of ≥ 0.3 units on slit-lamp biomicroscopic examination
- t) Confirmed worsening in the visual field mean deviation (MD) of \geq 2.5 dB compared to the MD determined at the exit of the COMPASS trial or the COMPASS XT trial

Document: TDOC-0056258 Version: 3.0; Most-Recent; Effective; CURRENT

Status: Effective Page 37 of 57

 Choroidal hemorrhage or choroidal effusion, defined as a choroidal effusion or detachment with at least a partially hemorrhagic component that obstructs vision or causes pain (including both peripheral and "kissing" choroidal detachments) lasting longer than 1 month

- v) Peripheral anterior choroidal effusion
- w) Maculopathy associated with hypotony
- x) Maculopathy associated with cystoid edema
- y) Hypotony (defined as IOP < 6 mmHg)
- z) Clinically significant hypotony, defined as IOP < 6 mmHg with any of the following findings:
 - i. Maculopathy
 - ii. Flat AC chamber requiring reformation
 - iii. Corneal folds
 - iv. Worsening of with-the-rule astigmatism by ≥ 1 diopter, or rotation of against-the-rule astigmatism to ≥ 1 diopter of with-the-rule astigmatism
 - v. Choroidal effusion requiring surgical drainage
 - vi. Suprachoroidal hemorrhage
 - vii. BCDVA loss of ≥ 2 lines from the best postoperative BCDVA

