11.3 Procedures for Recording and Reporting

Any ocular AEs occurring since the Exit visit from the COMPASS trial or the COMPASS XT trial (whichever was the last study visit) will be collected from the time of informed consent. Any pre-existing medical conditions or signs/symptoms present in the subject in the COMPASS trial or COMPASS XT trial are not considered AEs in the study and should be recorded in the Medical History section of the eCRF. However, a worsening of the pre-existing ocular AEs are considered AEs.

For each recorded event, the ADEs and SAEs documentation must include: date of occurrence, severity, treatment (if applicable), outcome, and assessments of the seriousness and causality. In addition, the Investigator must document all device deficiencies reported or observed with test and control articles on the Device Deficiency eCRF. The site must submit all available information on ADEs, SAEs, and device deficiencies to the Study Sponsor immediately as follows:

- All SAEs must be reported immediately (within 24 hours) of the Investigator's or site's awareness.
- ADEs that do not meet seriousness criteria and device deficiencies must be reported within 10 calendar days of the Investigator's or site's awareness.

A printed copy of the completed *Serious Adverse Event and Adverse Device Effect* and/or *Device Deficiency* eCRF must be included with product returns.

- Additional relevant information after initial reporting must be entered into the eCRF as soon as the data become available.
- Document any changes to concomitant medications on the appropriate eCRFs.
- Document all relevant information from Discharge Summary, Autopsy Report,
 Certificate of Death etc., if applicable, in narrative section of the Serious Adverse
 Event and Adverse Device Effect eCRF.

Note: Should the EDC system become non-operational, the site must complete the appropriate paper Serious Adverse Event and Adverse Device Effect and/or Device Deficiency Form. The completed form is emailed to the Study Sponsor at [contact] according to the timelines outlined above; however, the reported information must be entered into the EDC system once it becomes operational.

Document: TDOC-0056258 Version: 3.0; Most-Recent; Effective; CURRENT

Status: Effective Page 41 of 57

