12.4.4.2 Analysis Methods

Change in central endothelial cell density (within-eye) from baseline and percent change in central endothelial cell density will be summarized by visit. Baseline central endothelial cell density is the data collected at the COMPASS Study baseline visit. All references to baseline endothelial cell density data throughout this protocol refer to data from this visit. The proportion of subjects with central endothelial cell density less than 1000 cells/mm², the proportion of subjects with peripheral endothelial cell density less than 1000 cells/mm², the proportion of subjects with central endothelial cell density less than 500 cells/mm², and the proportion of subjects with central endothelial cell density less than 500 cells/mm², and the proportion of subjects with central endothelial cell loss over 30% from baseline will also be reported at these time points. A 95% exact binomial confidence interval will be presented for the proportions. The following statistics will be presented for change in central endothelial cell density at each visit: number of eyes, means, standard deviations, and the following percentiles: 0th, 5th, 25th, 75th,

Document: TDOC-0056258 Version: 3.0; Most-Recent; Effective; CURRENT

Status: Effective Page 46 of 57

95th, and 100th. A 95% confidence interval based on the t-distribution will be reported for the means at each visit. This analysis will be performed using central endothelial cell density data from visits in the COMPASS, COMPASS XT, and COMPASS XXT studies, where available, and using peripheral cell density data collected in this study. Summary statistics for peripheral (nasal) endothelial cell density will be presented for each study visit.

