13.3 Data Review and Clarifications

A review of CRF data to the subject's source data will be completed by the site monitor to ensure completeness and accuracy. After the CRFs have been completed, additional data clarifications and/or additions may be needed as a result of the data cleaning process. Data clarifications are documented and are part of each subject's CRF.

Document: TDOC-0056258 Version: 3.0; Most-Recent; Effective; CURRENT

Status: Effective Page 54 of 57

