### 4.3.16 Other Safety Outcomes

### 4.3.16.1 Best Corrected Visual Acuity (BCVA)

BCDVA (collected in letters read) will be summarized at each post-operative visit at which BCDVA is collected; change from baseline (COMPASS Baseline visit) will also be summarized at each postoperative visit at which BCDVA is collected. Data will be summarized based on the visual acuity score (letters read).

Best corrected visual acuity will also be converted to Snellen values and summarized categorically by the following groupings for each scheduled visit: 20/20 or better; 20/25 or better; 20/32 or better; 20/40 or better; worse than 20/40; missing; discontinued. Details for this conversion can be found in Appendix B.

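### The endpoint of losing 10 or more letters of BCVA is identified only from site adverse event reports; no proportion is planned from the ETDRS letters measured at every visit

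*Protocol*

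**What the plan says.** **How the endpoint is analysed.** Protocol 12.4.12.2 and SAP 4.3.12.2 use the same text. Both plan a listing of affected subjects with all their BCVA data from COMPASS, COMPASS XT and this study. Both say that such a loss will be reported as an AE, "so adverse event data will be the data source for this analysis". Neither section names a reference value, a proportion or an interval.

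**What is measured.** Protocol 10.2.6: "Perform monocular BCVA testing using ETDRS for the study eye at all study visits".

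**What makes a loss an AE.** Protocol 11.1.1(a) defines it as 2 lines (10 letters) or more "in comparison with the best BCDVA reported in COMPASS/COMPASS XT". Protocol 11.3 says that conditions or signs "present in the subject in the COMPASS trial or COMPASS XT trial are not considered AEs in the study", and then adds: "However, a worsening of the pre-existing ocular AEs are considered AEs".

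**What else is planned.**
- Protocol 12.4.2.2 and SAP 4.3.2.2 give counts, percentages and exact 95% intervals for all ocular AEs, by preferred term.
- SAP 4.3.16.1 summarises measured letters by visit, and "change from baseline (COMPASS Baseline visit) will also be summarized at each postoperative visit at which BCDVA is collected". It also gives Snellen groups.
- For low ECD, Protocol 12.4.4.2 plans proportions from measured values: "A 95% exact binomial confidence interval will be presented for the proportions".

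**Visual field mean deviation (MD).** Protocol 12.4.13.2 and SAP 4.3.13.2 class change from screening at more than 2.0 dB. SAP 4.3.16.6 classes change from screening at 2.5 dB or more.

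**The concern.** The study database will hold this study's letters, and the planned listing already draws on BCVA from the two earlier studies. The sponsor could therefore compute the endpoint for every measured eye. Instead, an eye becomes a case only if a site compares the new score with the best value from an earlier trial, recognises a loss of 10 letters and files an AE. Sites may also differ on a loss that was already present at exit from COMPASS or COMPASS XT. Section 11.1.1(a) would count it from the best earlier value, while 11.3 can be read as excluding it.

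What is at stake is a complete count of visual loss in a long-term safety study whose only product is description. The visual field point is smaller. Two tables of the same change would show different percentages under the same class names, and neither is marked as supportive.

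**Working it through.** The plan gives no figure to reproduce: there is no expected rate of BCVA loss, no AE capture rate, no MD standard deviation and no power calculation. The check is a comparison of sections, followed by illustrations on stated assumptions.

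**1. Does any planned analysis give a 10-letter-loss proportion from measured letters?**

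| Section | Source of cases | Reference | Output |
|---|---|---|---|
| Protocol 12.4.12.2, SAP 4.3.12.2 | AE reports | none stated; the AE definition uses best earlier BCDVA | listing |
| Protocol 12.4.2.2, SAP 4.3.2.2 | AE reports | as in the AE definition | rate with exact interval, by preferred term, not per visit |
| SAP 4.3.16.1 | measured letters | COMPASS baseline | letters, change and Snellen groups; no 10-letter class |

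None does. The second row has a rate but the same source, and a preferred term need not isolate the 10-letter threshold. The third row has the measured source, but a different reference and no such category.

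**2. What does each missed eye cost?** The proportion falls by 100/N percentage points. N is not fixed in advance: 215 is COMPASS XT enrolment, 374 is the maximum here, and 100 is an assumed low value.
- N = 100: 1.0 point
- N = 215: 100/215 = 0.47 point
- N = 374: 100/374 = 0.27 point

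**3. Illustration at N = 215.** Assumed true proportions are 5%, 10% and 20%, and assumed capture is 80% to 100%. Intervals are Clopper-Pearson 95%.

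| True cases | Cases at 80% capture | Percentage at full capture | Percentage at 80% capture |
|---|---|---|---|
| 11 | 11 × 0.8 = 8.8, about 9 | 5.1% (2.6 to 9.0) | 4.2% (1.9 to 7.8) |
| 22 | 22 × 0.8 = 17.6, about 18 | 10.2% (6.5 to 15.1) | 8.4% (5.0 to 12.9) |
| 43 | 43 × 0.8 = 34.4, about 34 | 20.0% (14.9 to 26.0) | 15.8% (11.2 to 21.4) |

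**4. The two AE rules on one eye (invented letters).** Best earlier score 83, score at COMPASS XT exit 72, score at year 10 70.
- Against the best earlier score: 83 − 70 = 13 letters, which meets 11.1.1(a).
- Already lost at exit: 83 − 72 = 11 letters.
- New since exit: 72 − 70 = 2 letters.

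The text does not settle whether this is an AE in this study. Part of the answer depends on whether the exit loss was an AE in the earlier trial, whose protocol is not before us.

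**5. MD cut-offs.** At exactly 2.0 dB both tables say no change, and at exactly 2.5 dB both say change. They differ only for absolute changes above 2.0 and below 2.5 dB. Assume that change is normal with mean m of 0, −1 or −2 dB and SD s of 2, 3 or 4 dB:
- Share classed as decrease in one table only = Φ((−2.0 − m)/s) − Φ((−2.5 − m)/s). The range is 4.3% (m = 0, s = 4) to 9.9% (m = −2, s = 2), or about 9 to 21 of 215 eyes.
- Adding the matching area between 2.0 and 2.5 dB gives 7.8% to 10.9% classed differently in either direction, or about 17 to 24 of 215.
- At m = −1, s = 3: 36.9% against 30.9% classed as decrease.

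**The case against.** **The endpoint does receive a rate.** A qualifying loss is an ocular AE, so it enters the AE tables with a percentage and an exact interval. This stands. A reader of the endpoint's own section might infer that the events appear in the report only as a listing; the ocular AE sections show otherwise. What remains is that those tables rest on the same reports, do not guarantee a row for this threshold and are not per visit.

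**Under-capture is hypothetical.** The plan says that such losses will be reported. Protocol 13.3 provides a review of CRF data against source that "will be completed by the site monitor to ensure completeness and accuracy", and mentions data cleaning. The Manual of Procedures and the Deviations and Evaluability Plan, which are not before us, may contain a check of letters against AEs. This also stands. A reader might infer that the count will be biased low, but the documents do not support that inference. They show only a dependence on site recognition that could be avoided.

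**AE data see what study visits cannot.** Ocular AEs reach back to exit from COMPASS or COMPASS XT, whereas other data are not collected retrospectively. Some subjects first attend at or after year 10, and unscheduled visits require AE collection but do not list BCVA testing. Losses that occurred and resolved in those gaps can appear only in AE reports. This stands, and it means that measured letters should supplement the AE source and not replace it.

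**The MD endpoint table is identifiable.** SAP 4.3.13 bears the endpoint's name and matches the protocol; 4.3.16.6 sits under other safety outcomes. One might infer that the protocol and SAP conflict on the endpoint, or that the reader cannot tell which table describes it. The headings answer both. Only the missing label remains.

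**Conclusion.** The point holds in a limited form. AE reports are the only named source for identifying this endpoint, its own section gives only a listing, and no analysis turns the measured letters into a proportion with a 10-letter loss. A more complete and less report-dependent derivation is available from data already planned. That conclusion rests on the text alone.

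The size of any under-count is unknown. The fall from 10.2% to 8.4% at 215 eyes rests on an assumed 10% rate and 80% capture, and is an illustration, not an estimate. Nothing is tested in this study, so no error of inference arises. The change should be made because it is cheap and bears on a named safety endpoint.

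The two MD cut-offs are a minor labelling matter. The 7.8% to 10.9% of eyes classed differently depends on the assumed normal model and its range of means and SDs.

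**What to change.** **In Protocol 12.4.12.2 and SAP 4.3.12.2:**
- Derive the loss of 10 or more letters by program from measured letters, against the best COMPASS/COMPASS XT BCDVA that Protocol 11.1.1(a) already uses.
- For each visit, report n/N (N being eyes with measured BCVA), the percentage and an exact 95% interval.
- Keep the AE listing and reconcile it with the derived cases.
- Flag losses already present at exit from COMPASS or COMPASS XT.
- Report cases found only in AE data separately, because losses that resolved before enrolment or between visits cannot be seen in the letters.

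**In SAP 4.3.16.6:** label the 2.5 dB table as supportive, or reconcile it with the endpoint categories in SAP 4.3.13.2 and Protocol 12.4.13.2.

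**Cost.** New wording and a little programming; no new data. There are two limits to state in the report. A best-earlier-value reference brings some regression to the mean, so part of the counted loss will be measurement noise; the exit flag helps interpretation but does not remove this. And measured letters cover study visits only.

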12.4.13 Change in Visual Field Mean Deviation (MD)

12.4.13.1 Statistical Hypotheses

No hypothesis testing of the endpoint is planned.

12.4.13.2 Analysis Methods

Change in visual field mean deviation at each visit postoperative as compared to the recorded value at the COMPASS screening visit will be reported. Observed values and change from screening values will be presented descriptively (N, mean, median, standard deviation, standard error, minimum, and maximum) at each study visit for each device.

Counts and percentages of subjects will be presented according to the following categories: increase > 2.0 dB; no change (-2.0 to 2.0 dB); decrease > 2.0 dB. Denominators will consist of the number of subjects with non-missing visual field data at both time points.

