5 INTRODUCTION

5.1 Rationale and Background

The COMPASS trial was a prospective, randomized, comparative multicenter study to assess the safety and effectiveness of the CyPass Micro-Stent in subjects with primary open angle glaucoma who were undergoing cataract surgery. In the study, a total of 505 subjects were randomized to one of two treatment groups, as follows: the CyPass group underwent cataract surgery and received the CyPass Micro-Stent, while the Control group underwent cataract surgery alone. All subjects randomized were followed for 24 months postoperatively, Vold 2016.

The study was performed in 2 phases. During the initial phase, 75 subjects were randomized. After FDA review of 3-month or longer postoperative data on these subjects, approval was granted for enrollment and randomization of the remaining 430 subjects in the study expanded phase. Enrollment in the initial study phase began in September 2009 and ended in August 2010. Enrollment in the expanded phase of the study began in July 2011 and the last study subject was randomized in March 2013.

The COMPASS XT trial was designed to collect safety data beyond 24 months postoperatively for subjects who completed the COMPASS trial until 60 months. Study enrollment was initiated April 2016 and the last subject visit occurred in April 2018, lanchulev 2019, and Reiss 2019.

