- aa) Elevated mean $IOP \ge 10$ mmHg than the qualifying baseline mean IOP at or after 1 month postoperative
- bb) CyPass device obstructed by iris, vitreous, lens, fibrous overgrowth, fibrin, or blood
- cc) CyPass device malposition positioning after deployment such that there is a clinical sequelae resulting from device position including, but not limited to:
 - i. Secondary surgical intervention to modify device position (eg, repositioning, proximal end trimming or explantation)
 - ii. Corneal endothelial touch by device
 - iii. Corneal edema leading to loss of BCDVA > 2 lines in comparison with preoperative BCDVA

Document: TDOC-0056258 Version: 3.0; Most-Recent; Effective; CURRENT

Status: Effective Page 38 of 57

iv. Progressive ECL, defined as ongoing reduction in endothelial cell count of 30% or more relative to the screening ECD value, where 'ongoing reduction in endothelial cell count' is defined as losses continuing after 6 Months

- v. Erosion of device through sclera
- vi. Device obstruction requiring secondary surgical intervention
- dd) CyPass device dislodgement or movement, without sequelae, where device movement is defined as a change by at least 1 in the number of CyPass rings visible that is not attributable to variations in gonioscopic viewing angle or illumination, changes in angle anatomy due to concomitant findings such as resolution of hyphema, change in AC depth, or development of focal peripheral anterior synechiae
- ee) CyPass device explantation associated with CyPass placement and stability
- ff) CyPass device explantation NOT associated with CyPass placement and stability
- gg) Unplanned ocular surgical reintervention associated with CyPass placement and stability
- hh) Unplanned ocular surgical reintervention NOT associated with CyPass placement and stability (other than posterior capsulotomy)
- ii) Significant ptosis
- jj) Atrophy/phthisis
- kk) Wound dehiscence/leak (persistent aqueous leak or fistula formation)
- ll) Subconjunctival hemorrhage
- mm) Chronic pain in the study eye
- nn) Significant foreign body sensation
- oo) IOL subluxation

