### 4.3.16.6 Visual Field Loss Mean Deviation Testing

The visual field mean deviation (dB) testing data will be summarized for each visit. A categorical summary of changes from screening will be presented using the following three categories: Increase ( $\geq 2.5$  dB), No Change (-2.5 < dB to < 2.5 dB), or Decrease ( $\leq -2.5$  dB).

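### Visual field MD change, and one supportive BCDVA change summary, are measured only from visits before the cataract surgery done at implantation, so surgical gain and later loss cannot be separated

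*Protocol*

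**What the plan says.** **Visual field MD, a listed safety endpoint.** Protocol 12.4.13.2, repeated in SAP 4.3.13.2: "Change in visual field mean deviation at each visit postoperative as compared to the recorded value at the COMPASS screening visit will be reported". The categories are "increase > 2.0 dB; no change (-2.0 to 2.0 dB); decrease > 2.0 dB". SAP 4.3.16.6 adds a second table: "A categorical summary of changes from screening will be presented using the following three categories", this time with cut-offs at 2.5 dB.

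**BCDVA, under Other Safety Outcomes.** SAP 4.3.16.1: "change from baseline (COMPASS Baseline visit) will also be summarized at each postoperative visit at which BCDVA is collected".

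**The operation.** Protocol 5.1 on COMPASS: "the CyPass group underwent cataract surgery and received the CyPass Micro-Stent".

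**References used elsewhere (Protocol 11.1.1).**
- Item (t) makes a confirmed MD worsening of 2.5 dB or more an adverse event, "compared to the MD determined at the exit of the COMPASS trial or the COMPASS XT trial".
- Item (a) is "BCDVA loss of 2 lines (10 letters) or more on the ETDRS chart in comparison with the best BCDVA reported in COMPASS/COMPASS XT".
- Item (b) uses the best BCDVA across the studies, and item (z)(vii) the best postoperative BCDVA.
- Item (cc)(iii), a malposition example, reads "Corneal edema leading to loss of BCDVA > 2 lines in comparison with preoperative BCDVA".

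The listed endpoint on BCVA losses of 10 letters or more (Protocol 12.4.12.2) is built from adverse event data, and so inherits the item (a) reference.

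**The concern.** COMPASS enrolled people who were undergoing cataract surgery, and every eye eligible here had that surgery with the stent. The COMPASS screening and baseline visits must therefore be preoperative. The documents do not say so in one sentence, but no other reading fits. An eye's change from those visits is the effect of cataract removal plus whatever has happened since. Only the second part bears on the long-term safety of the device.

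In COMPASS both arms had cataract surgery, so the surgical part could cancel between arms. This study is single-arm with no control (Protocol 7.1 and 7.4), and nothing removes it. No planned change table for MD or BCDVA starts from a postoperative visit. If surgery improved the measurement, an eye that has since lost field or acuity can be tabulated as unchanged or improved, and the mean change is shifted the same way.

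**Working it through.** The plan has no figure of its own to reproduce: the 374 is a cohort count, and no gain, loss or SD is given for MD or BCDVA. The check compares the reference visits and then shows how an offset would act.

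**1. References side by side**

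| Analysis | Reference | Before or after surgery |
|---|---|---|
| MD endpoint (Protocol 12.4.13.2, SAP 4.3.13.2) | COMPASS screening | Before |
| Second MD table (SAP 4.3.16.6) | Screening | Before |
| BCDVA change (SAP 4.3.16.1) | COMPASS baseline | Before |
| MD adverse event, item (t) | COMPASS or COMPASS XT exit | After |
| BCVA-loss endpoint, via item (a) | Best in COMPASS/COMPASS XT | Includes any postoperative gain |
| Sight-threatening BCDVA loss (11.1.2) | Best BCDVA | Includes any postoperative gain |

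**2. MD threshold.** Let g be the gain at surgery and L the later loss. Tabulated change = g − L.
- 2.0 dB rule: decrease if g − L < −2.0, that is L > 2.0 + g.
- 2.5 dB rule (SAP 4.3.16.6): decrease if g − L ≤ −2.5, that is L ≥ 2.5 + g.

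With g assumed, because the documents give no value:

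| g (dB) | L must exceed (2.0 dB rule) | L must reach (2.5 dB rule) |
|---|---|---|
| 0 | 2.0 | 2.5 |
| 0.5 | 2.5 | 3.0 |
| 1.0 | 3.0 | 3.5 |
| 1.5 | 3.5 | 4.0 |
| 2.0 | 4.0 | 4.5 |

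**3. Share of eyes classed as a decrease (2.0 dB rule).** Assume change is normal with mean g − L, a mean later loss L of 3 dB, and the same SD at every g. Share = Φ((−2.0 − (g − L))/SD). For g = 1.0 and SD = 2: Φ((−2.0 + 2.0)/2) = Φ(0) = 50%.

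| g (dB) | SD 2 dB | SD 3 dB |
|---|---|---|
| 0 | 69% | 63% |
| 0.5 | 60% | 57% |
| 1.0 | 50% | 50% |
| 1.5 | 40% | 43% |
| 2.0 | 31% | 37% |

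These are illustrations, not estimates for this cohort.

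**4. BCDVA.** For a later loss of 10 letters and an assumed gain of 5, 10 or 15 letters, the baseline table shows 5 − 10 = −5, 10 − 10 = 0, or 15 − 10 = +5.

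One eye on the SAP Appendix B scale: 80 letters (20/50) before surgery, 100 (20/20) after, 85 (20/40) later. The SAP 4.3.16.1 table records 85 − 80 = +5. Item (a) records at least 100 − 85 = 15 letters lost, so the eye is an adverse event and enters the BCVA-loss listing. Fifteen letters is 3 lines, so if the loss persists at exit it is also a sight-threatening event.

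**The case against.** A reader might infer that the plan hides later loss on two safety outcomes. The documents do not support that.

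- **Acuity.** The listed endpoint and the sight-threatening event use best BCDVA, and the listing shows each affected subject's acuity from all three studies. The eye in step 4 is caught. Only a supportive table shows it as +5, and that SAP section also tabulates letters read and Snellen groups by visit. This stands: the acuity point is confined to one summary.
- **Item (cc)(iii).** It is one example in a non-exhaustive list, and corneal edema and acuity loss are separate items. Its reference differs from the others and needs reconciling, but it does not remove a loss from the safety data.
- **MD.** Item (t) measures from a postoperative exit value and is reported among ocular adverse events with an exact interval. Observed MD is also summarised by visit. This is real but partial cover. Item (t) misses loss under 2.5 dB, loss before the exit visit and unconfirmed loss. Some subjects may have only one visit in this study (Protocol 7.1), and Table 3–1 lists no repeat field. Visit means are not within-eye change, and the contributing eyes differ between visits.
- **Direction.** A reader might also take the MD gain as established. The documents give neither its size nor its sign. If it were zero the offset would vanish; if negative, it would run the other way.
- **Consequence.** The study is descriptive, its objective is the corneal endothelium, and a preoperative baseline matches the ECD analysis. This is a reason to keep the existing tables, not a reason to have no postoperative reference.

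**Conclusion.** The point holds in a limited form. The MD endpoint and the SAP 4.3.16.1 BCDVA change summary have no postoperative reference, and without a control arm they cannot separate the surgical effect from later change. This follows from the documents, given the inference that the screening and baseline visits were preoperative.

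The size is conditional. An assumed MD gain of 0.5 to 2.0 dB raises the later loss needed for the decrease category from more than 2.0 dB to more than 2.5 to 4.0 dB. In the step 3 illustration, at SD 2 dB, it cuts the share so classed from 69% to between 60% and 31%. The listed BCVA-loss endpoint and the sight-threatening BCDVA event are unaffected, and item (t) limits the exposure for MD. The matter is worth correcting because the remedy is cheap and because MD change is a listed endpoint.

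**What to change.** 1. **Keep** change from screening (MD) and from baseline (BCDVA), labelled as preoperative references.
2. **Add** to Protocol 12.4.13.2 and SAP 4.3.13.2 and 4.3.16.6 the MD change and category tables from the COMPASS 24-month exit value. Add to SAP 4.3.16.1 a BCDVA change table from the same visit. State the number of eyes with a value at both times.
3. **For MD, also show** change from the COMPASS/COMPASS XT exit value, so that the table lines up with item (t). This should not be the only added reference, because its timing differs: 24 months for those not in COMPASS XT, later for those who were.
4. **Do not use best BCDVA as the reference for a mean change.** The maximum of several readings is too high by chance. With five readings and an assumed test-retest SD of 3 to 5 letters, it exceeds the true value by about 1.16 SD, or 3.5 to 5.8 letters, with no real loss. Best BCDVA suits an adverse event trigger.
5. **Reconcile** the MD cut-offs (2.0 dB in SAP 4.3.13.2, 2.5 dB in SAP 4.3.16.6), or state why both are wanted. Reconcile the preoperative BCDVA reference in item (cc)(iii) with those in items (a), (b) and (z)(vii).

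The cost is wording in two documents and a few tables. Item (t) already relies on exit MD and Protocol 12.4.12.2 already draws on BCVA from all three studies, so no new collection should be needed. Eyes without a 24-month value drop out of the tables based on that visit, and loss before 24 months shows only in the tables from screening or baseline, which is why those should stay.
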